11.2 Table 1: Table of Assessments/Forms

Assessment	Time Needed to Complete (only for ppt assessments)	Screening	Random- ization	Baseline	Day 30	Day 90	Day 180	Day 210	As Needed
		(Index ED Visit/Enrollment) – Virtual or In-person			Phone, Virtual, or In- person	Phone, Virtual, or In- person	Phone, Virtual, or In- person	Phone, Virtual, or In- person	
Screening									
Screening Enrollment Form	5 mins	X							
Prisoner Status Assessment	2 mins	X							
Demographics	5 min	X							
Patient Health Questionnaire-9	2 mins	X			X	X	X	X	
Screening Exit Survey	10 mins	X							
Written Informed Consent	30-45 mins	X							
Inclusion/Randomization and Study Visits									
Study Enrollment Form			X						
Visit Documentation				X	X	X	X	X	
Locator Information Form	5-10 mins			X	[X]	[X]	[X]	[X]	
Overdose Information	3 mins			X	X	X	X	X	
Urine Drug Test	5 mins			X	X	X	X	X	
Overdose Risk Behavior Checklist	3 mins			X	X	X	X	X	
Harm Reduction Checklist	3 mins			X	X	X	X	X	
Step 2-7 Assessment Form (SAF 2-7)	4 mins			X	X	X	X	X	

Assessment	Time Needed to Complete (only for ppt assessments)	Screening	Random- ization	Baseline	Day 30	Day 90	Day 180	Day 210	As Needed
		(Index ED Visit/Enrollment) – Virtual or In-person			Phone, Virtual, or In-person				
MOUD Confirmation Assessment (confirmed via objective measures)	3 mins				X	X	X	X	
MOUD Current Status	2 mins			X	X	X	X	X	
Readiness Ruler	1 min			X	X	X	X	X	
Alcohol and Substance Use History (PhenX Tier 1)	10 mins			X					
Timeline Follow-Back (7 day)	3 mins			X	X	X	X	X	
DSM-5 Checklist	5-10 mins			X	X	X	X	X	
ED MOUD Administration (obtained from EMR)				X					
End of Treatment							X		X
Assessment of Recovery Capital	8 mins			X	X	X	X	X	
Chronic Pain History	1 min			X					
Tobacco Use History	2 mins			X					
Fagerstrom Test for Nicotine Dependence	2 mins			X					
Cannabis Use Assessment	1 min			X			X	X	
Quality of Life	3 mins			X	X	X	X	X	
Crime and Criminal Justice	3 mins			X	X	X	X	X	
Treatment Satisfaction Form	5 mins							X	X
Administration or Non-Visit Based Forms									
Mental Health Follow-up Assessment	2 mins								X
ED Visits and Hospitalizations	5 mins								X
Screening Approach	1 min								X
Contact Log	5 mins								X
Death Form	5 mins								X
Protocol Deviation and Review Forms	5 mins								X
Study Completion Form	2 mins							X	X
Inventory – Supplies Form	5 mins								X
TAU Characterization Form	15-20 mins								X
Peer Characterization Survey	5-10 mins								X
Remote Assessments									
Mobile Weekly Surveys	3-5 mins				X ^b	X ^b	X ^b	X ^b	
PILOT Intervention									
PILOT Intervention Activities Log	1-5 mins			X	X	X	X	X	
Supervisor Log	3-5 mins							X	
Rolling Progress Note	2-10 mins							X	

Notes: ^b=administered weekly

[X]= assessment is reviewed and updated as needed

11.3 Screening Measures

11.3.1 Screening Enrollment

Individuals will meet with a member of the research staff to be evaluated for study eligibility. This assessment will be conducted after verbal consent, and before enrollment into the study. It will include questions about overdose involving opioids, age, reason for ED visit, and other questions that may exclude an individual from the study. If the individual had an overdose in the past 30 days, the Screening Enrollment Form asks whether the overdose was accidental or intentional. If the individual's answer is "intentional", the individual will be excluded from study participation, but the response will also prompt study staff to have the individual evaluated by the study clinician for active suicidal ideation and trigger completion of the Mental Health Follow-Up Assessment Form.

The Screen Enrollment form also documents eligibility during the screening phase, before written informed consent is obtained. Eligibility will be re-assessed prior to randomization, and then continually as appropriate. Only participants who continue to meet study eligibility criteria will be allowed to continue with the screening process and randomization.

11.3.2 Prisoner Status Assessment

Individuals approached in the ED will complete a Prisoner Status Assessment to determine that they do *not* meet the OHRP definition of prisoner. If they do meet the definition, they will not be able to enter the study, but will continue to receive TAU as established in the ED. The individual is not assigned a number and no data is retained from the encounter. If the individual does *not* meet the definition of prisoner, they will be invited to learn more about the study and complete the informed consent process.

11.3.3 Demographics Form

The PhenX Demographics form collects information about demographic characteristics of the participant, including sex, date of birth, ethnicity, race, education, employment status, and marital status. A study-specific demographics form collects information about homelessness, criminal justice supervision, employment, insurance status, living arrangements, etc.

11.3.4 Alcohol and Substance Use History (PhenX Tier 1)

The Substance Abuse and Addiction Collection of the PhenX Toolkit (<http://www.phenxtoolkit.org/>) includes measures that are being adopted across NIDA-funded research. The Core Tier 1 collection includes measures for substance use history, such as age of onset, lifetime use for alcohol, tobacco, and other substances. The most up to date version of the PhenX questions will be used (Version 20, dated December 2019).

This form will be administered at baseline only and will assess lifetime and past 30 day use of alcohol, non-medical use of prescribed controlled substances, non-prescribed pharmaceutical prescription drugs and illicit drug use. It will also assess, as applicable, age of first use. For the baseline assessment, this form will be administered contiguous with the 7-day TLFB to avoid repeat assessment of drug use.

11.3.5 Informed Consent and Research Authorization

Participants will review and sign the IRB-approved consent form and any other related documents (e.g., Research Authorization, HIPAA authorization) in accordance with IRB requirements either in person or electronically through REDCap eConsent. Procedures for obtaining informed consent and related authorizations are detailed in **Sections 10.1 and 10.2**. Only patients who continue to meet study eligibility criteria will be allowed to continue to the enrollment phase.

11.3.6 Participant Eligibility Summary and Randomization

The Patient Eligibility Summary and Randomization form collects information regarding eligibility. Only participants who continue to meet study eligibility criteria will be allowed to continue with randomization.

11.3.7 Screening Exit Survey

Patients who do not pass the screening instrument and/or are not interested in participating in the study will have the option to complete a brief, de-identified, interviewer-administered survey asking about reasons for ED visit, demographics, substance use history, overdose history, Narcan availability, and reasons for study decline (as applicable). Compensation will be provided for completing this survey, but as the survey will not be associated with identifying information, it will be completed with an approved waiver of written consent.

11.4 General Measures

11.4.1 Patient Health Questionnaire (PHQ-9)

The Patient Health Questionnaire (PHQ-9) [39] will be used to assess depressive symptoms, including suicidal ideation. If the participant responds to “Thoughts that you would be better off dead, or of hurting yourself in some way” with any response other than “Not at all”, it will trigger a requirement to provide the participant with Suicide Hotline information and other mental health resource information per the MOP. When the response is recorded at screening/baseline, the study clinician, or in cases where the study clinician is not reasonably available, an available non-study clinician at the site will be notified. All sites should monitor participant responses to this PHQ-9 question, as well as participant spontaneous expression of potential suicidal/homicidal ideation and have procedures in place to ensure patient safety. In all cases, participant mental health follow-up should occur according to site-specific SOPs. For any endorsement of potential suicidal ideation reported on the PHQ-9, completion of the Mental Health Follow-up Assessment form will be required.

11.4.2 Visit Documentation

This form documents visit attendance, non-visit attendance, and missed visits. This form additionally captures whether any ED visits or hospitalizations occurred since the last study visit, and if so, it triggers the ED Visit and Hospitalization form. This assessment has been recently developed to document visits that could occur out of window, off site, or missed due to COVID-19. This is a visit-based form expected at all visits that would typically have a regular missed visit form. If a visit is missed for any reason, this form will capture the reason a study visit was missed. Completing this form and indicating that the visit was not attended will remove the requirement

for all assessments scheduled for that visit. Active tracking and follow-up should be performed for all missed visits. The form also captures specific data collection settings if applicable (such as in clinic, off-site, remote, or in a controlled environment).

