11.4.12 ED Visits and Hospitalizations

Data will be collected on health care utilization (inpatient and outpatient) between the index and 30-, 90-, 180-, and 210-day assessments and on an as needed basis for spontaneous reporting that occurs between study visits. ED visits and hospitalizations will be collected through self-report and review of participant electronic medical records.

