### 17.1.8 Safety Outcomes

**Table 39: Summary of Hospitalizations by Treatment Arm**

		Treatment Arm		
Study Period 		TAU (N=XX)	PILOT (N=XX)	Total (N=XX)
Treatment Period	Number of participants with at least one hospitalization 	N (X.x%)		
	Number of participants with at least one hospitalization related to substance use 	N( X.x%)		
	Related to overdose 			
	Related to withdrawal 			
	Related to intoxication 			
	Number of hospitalizations	N	N	N
	Number of hospitalizations per participant 			
	0			
	1			
	2			
Follow-up Period	3			
	4			
	5 or more			
	Number of participants with at least one hospitalization 			
	Number of participants with at least one hospitalization related to substance use 			
	Related to overdose 			
	Related to withdrawal 			
	Related to intoxication 			
	Number of hospitalizations			
	Number of hospitalizations per participant 			
	0			
	1			
	2			
	3			
	4			
	5 or more			

Hospitalizations are as captured on the ED Visits and Hospitalization (EDH) form.

The treatment period extends from day of randomization to Study Day 180. After that, the follow-up day extends to Study Day 210.

The percentage is calculated with the denominator as the number of participants randomized.

The percentage is calculated with the denominator as the number of participants with at least one hospitalization.

The percentage is calculated with the denominator as the number of participants with at least one hospitalization related to substance use.

The hospitalization related to substance use may be due to multiple reasons.

Listing 1: Hospitalizations by Treatment Arm								
Treatment Arm = TAU								
Site	Participant ID	Date of Randomization	Hospitalization Date	Discharge Date	Primary Diagnosis/Complaint	Secondary Diagnosis/Complaint	Tertiary Diagnosis/Complaint	Outcome
xxxxx	xxxxxxxxxxxx	mm/dd/yyyy	mm/dd/yyyy	mm/dd/yyyy	xxxxxxxx	xxxxxxxx	xxxxxxxx	Recovering/resolving Recovered/resolved Recovered/ resolved with sequelae Not recovered/not resolved Fatal Unknown

Listing 1: Hospitalizations by Treatment Arm								
Treatment Arm = PILOT								

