**Table 42: Summary of Suicide Risk by Treatment Arm**

		Treatment Arm		
Visit	Over the last two weeks, how often have you been bothered by thoughts that you would be better off dead, or of hurting yourself in some way? 	TAU (N=XX)	PILOT (N=XX)	Total (N=XX)
Screening	Responses 			
	Not at all			
	Several days			
	More than half the days			
	Nearly every day			
Day 30	Responses 			
	Not at all			
	Several days			
	More than half the days			
	Nearly every day			
Day 90	Responses 			
	Not at all			
	Several days			
	More than half the days			
	Nearly every day			
Day 180	Responses 			
	Not at all			
	Several days			
	More than half the days			
	Nearly every day			
Day 210	Responses 			
	Not at all			
	Several days			
	More than half the days			
	Nearly every day			

 This question is asked as part of the 9-item version of the Patient Health Questionnaire (PHQ-9).

 The percentage of the number of responses is calculated with the number randomized as the denominator. The percentage for individual responses is calculated with the number of responses as the denominator.

Listing 4: Suicide Risk by Treatment Arm					
Treatment Arm = TAU					
Site	Participant ID	Date of Randomization	Date of Assessment	Visit	Thoughts You are Better Off Dead or of Hurting Yourself
xxxxx	xxxxxxxxxxxx	mm/dd/yyyy	mm/dd/yyyy	Screening/ Day 30/ Day 90/ Day 180/ Day 210	Not at all/ Several days/ More than half the days/ Nearly every day

All visits with PHQ-9 completed are included for participants who indicate suicide risk at any visit. For PHQ-9 suicide risk is indicated by a response of "Several days", "More than half the days" or "Nearly every day".

Listing 4: Suicide Risk by Treatment Arm					
Treatment Arm = PILOT					
Site	Participant ID	Date of Randomization	Date of Assessment	Visit	Thoughts You are Better Off Dead or of Hurting Yourself
xxxxx	xxxxxxxxxxxx	mm/dd/yyyy	mm/dd/yyyy	Screening/ Day 30/ Day 90/ Day 180/ Day 210	Not at all/ Several days/ More than half the days/ Nearly every day

All visits with PHQ-9 completed are included for participants who indicate suicide risk at any visit. For PHQ-9 suicide risk is indicated by a response of "Several days", "More than half the days" or "Nearly every day".

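### SAP Tables 39–40 put participants who died, withdrew or were permanently lost in the zero-event row when no ED visit or hospitalization is on record, even for time after their safety window closed

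*Protocol*

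**What the plan says.** **Denominator.** Footnote 2 of SAP Table 39 reads "The percentage is calculated with the denominator as the number of participants randomized", and footnote 2 of Table 40 says the same for ED visits. In both tables it governs the row for participants with any event and the rows for 0, 1, 2 and higher counts. Each table has a block for the treatment period, from randomization to Day 180, and one for the follow-up period, to Day 210. SAP 8.1 and 8.2 plan summaries and listings by arm. No test, no person-time and no category for unknown status is planned.

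**Safety window.** SAP 3.2.5 ends a participant's window at the Day 210 visit, or when that visit's window lapses, or once the site confirms that participation is over for good, with death and withdrawal of consent as its examples.

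**How events are found.** Protocol 11.4.12 states that "ED visits and hospitalizations will be collected through self-report and review of participant electronic medical records", and it also provides for collection "on an as needed basis for spontaneous reporting that occurs between study visits". The Visit Documentation form (V07) is the prompt at visits: "This form additionally captures whether any ED visits or hospitalizations occurred since the last study visit, and if so, it triggers the ED Visit" (that is, the form abbreviated EDH in the SAP). Protocol Table 1 lists the EDH form under "Administration or Non-Visit Based Forms", marked as needed.

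**Missed visits.** Protocol 11.4.2 says "Completing this form and indicating that the visit was not attended will remove the requirement"; the sentence goes on to limit this to the assessments scheduled for that visit. The same section adds: "Active tracking and follow-up should be performed for all missed visits".

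**The concern.** A zero in Tables 39–40 can mean two things: the participant's status was established and there was no event, or the participant was no longer being observed and nothing turned up. The tables do not separate them. In the follow-up block, the denominator also includes people whose safety window had already closed.

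ED visits and hospitalizations are two of the five targeted safety events in SAP 3.2.6. Descriptive summaries of these events go to the DSMB (SAP 11.1), which may recommend halting for safety (Protocol Appendix A, 1.0 C). If permanent loss differs by arm, the arm with less follow-up can look safer at equal true risk.

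A difference is plausible. Protocol 10.12 expects trouble keeping follow-up high. SAP 6.2 has PILOT peers attempting contact at least weekly, and Protocol Appendix A describes their efforts to re-engage participants who drop out of contact. TAU has no study peer. Plausible is as far as the documents go.

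**Working it through.** There is no figure in the plan to reproduce, so the check has two parts: where the tables place different participants, and how the apparent result would move under stated assumptions.

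**Step 1: placement.** Take a participant with no recorded event.

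| Course | Is the gap covered later? | Place in Tables 39–40 |
|---|---|---|
| Misses Day 90, attends Day 180 | Yes, V07 asks back to the last visit | Zero row, correctly |
| Last seen Day 30, never found again | Only by record review or a spontaneous report; the window runs until the Day 210 visit window lapses | Zero row in both periods |
| Withdrawal or death confirmed on Day 60 | No; the window has closed | Zero row in both periods |

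In the third case the window covers 60 of 180 treatment-period days (33%) and 0 of 30 follow-up days. Later events fall outside the SAP's own window, so the follow-up zero stands whatever the records contain. For a death the zero is literally true, but the person was not at risk.

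**Step 2: illustration.** Inputs:

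- About 75 per arm, from about 150 randomized 1:1 (Protocol 2.3).
- p, the true proportion with an event, equal in both arms. The low value is 19/230 = 8.3%, the return-to-hospital figure for the predecessor program in Protocol 4.2 (observational, engaged clients). The values 30% and 50% are assumptions.
- f, the share followed: 80% in PILOT and 60% in TAU, assumed.
- e, the share of events among those not followed that is still captured through records or spontaneous reports, assumed from 0 to 1.

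Apparent proportion = p × [f + (1 − f) × e]. The ratio PILOT/TAU does not depend on p:

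- e = 0: 0.80 / 0.60 = 1.33
- e = 0.5: (0.80 + 0.20 × 0.5) / (0.60 + 0.40 × 0.5) = 0.90 / 0.80 = 1.125
- e = 0.8: 0.96 / 0.92 = 1.04
- e = 1: 1.00

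Apparent percentages, PILOT vs TAU, with the difference in points (calculated before rounding):

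| e | p = 8.3% | p = 30% | p = 50% |
|---|---|---|---|
| 0 | 6.6 vs 5.0 (1.7) | 24.0 vs 18.0 (6.0) | 40.0 vs 30.0 (10.0) |
| 0.5 | 7.4 vs 6.6 (0.8) | 27.0 vs 24.0 (3.0) | 45.0 vs 40.0 (5.0) |
| 0.8 | 7.9 vs 7.6 (0.3) | 28.8 vs 27.6 (1.2) | 48.0 vs 46.0 (2.0) |
| 1 | 8.3 vs 8.3 (0) | 30.0 vs 30.0 (0) | 50.0 vs 50.0 (0) |

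With follow-up of 80% vs 70%, the ratios for e = 0, 0.5 and 0.8 are 1.14, 1.06 and 1.02. With 80% vs 50% they are 1.60, 1.20 and 1.07. With equal follow-up and equal capture the ratio is 1.00. If TAU were the better-followed arm, the direction would reverse.

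The model treats each person as either followed or not. Someone lost partway contributes some observation, so the e = 0 row is the extreme case.

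**The case against.** The strongest reply is that the plan has several routes to an event that need no attendance at the missed visit. The waiver stops at assessments scheduled for that visit, and the EDH form is not one of them. Record review is a planned source, missed visits must be actively tracked, and the V07 question reaches back over a skipped visit. All of this stands. It confines the problem to participants who never return.

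A reader might infer that a missed visit cancels every form, that everyone lost is therefore recorded as event-free, and that the comparison is biased. The documents do not support that. Bias needs both unequal permanent loss and incomplete capture, and neither is given. Nor does any section say that PILOT peers report ED visits or hospitalizations to the EDH form, so extra reporting through the peers is an inference.

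A reader might also see an inconsistency with Table 42, where "The percentage for individual responses is calculated with the number of responses as the denominator". That is a weak comparison. Table 42 tabulates answers to one questionnaire item per visit, where a response denominator is natural, and the same footnote first sets the number of responses against the number randomized.

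Finally, the tables are descriptive, and disposition, attendance and missed visits are shown by arm (Tables 6, 8, 10, 12 and 14). This stands only in part. Those tables do not show whose ED or hospital status is unknown in a given period, so a reader cannot correct Tables 39–40 from them. For deaths, Protocol 11.6.2 turns to locator contacts when a participant is lost; no equivalent is written for ED visits and hospitalizations. The scope and timing of record review for non-attenders are not stated either.

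**Conclusion.** The point holds in a limited form. Dividing by all randomized places people who died, withdrew or were permanently lost, and for whom no event was found, in the zero row. This includes periods after SAP 3.2.5 has closed their window. That much follows from the documents and needs no assumption about record review.

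Whether it distorts the comparison between arms is conditional on permanent loss differing by arm and on capture being incomplete. The documents give neither quantity, so the bias is possible but not shown and cannot be sized from them. Under the assumed 80% vs 60% follow-up, the apparent ratio runs from 1.33 with no capture to 1.00 with full capture. At the 8.3% rate and no capture, the gap is 1.7 points, or about 1.2 participants per 75 (5.0 vs 3.7 before rounding). At an assumed 30% it is 6.0 points, or 4.5 participants (18.0 vs 13.5).

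**What to change.** In SAP 8.1–8.2 and Tables 39–40, keep the randomized N and add, per period and arm:

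- the number still under observation;
- the person-time observed, from randomization to the last attended visit with the V07 question answered, or to the study-completion date, cut at the period end;
- events per 100 person-months;
- in place of the zero row, two rows: ascertained with none, and not ascertained.

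The SAP should say which end date applies to whom. For someone lost without confirmation, Protocol 11.4.14 has the Study Completion form filled in after the Day 210 window lapses. Using that date would credit time nobody covered, so the last attended visit should apply. The study-completion date suits withdrawal and death. Events dated after observation ended can stay in the counts and listings but should be left out of the rate, so that numerator and denominator cover the same time.

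Do not build this on record-review dates, and do not add a re-analysis without spontaneous reports. The documents do not show that a review date or a report source is collected. A sentence on which records are reviewed, and whether this covers people who no longer attend, would help readers judge the not-ascertained row.

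The cost is slightly longer tables and a little programming from visit and study-completion dates.

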11.4.3 Locator Information Form

A locator form is used to obtain information to assist in finding participants during treatment and at 30-, 90-, and 180-day phone assessments as well as a 210-day follow-up assessment. This form collects the participant's current address, email address, and phone numbers (updated frequently or as needed) as well as information such as social security number, driver's license number and other information to aid in searches of public records. To facilitate locating participants and keeping up-to-date phone numbers if direct contact efforts are unsuccessful, addresses and phone numbers of family/friends or other contacts who may know how to reach the participant are collected (minimum of two required to be eligible for the study). This information will be collected at after obtaining informed consent and will be updated at each visit or whenever the participant reports a change in locator information. No information from this form is used in data analyses. At screening/baseline, at least two contacts must be identified.

